#### 3.9.1.2 Objectives Assessed in Both Exposure Groups (Remaining Objectives)

The risk of confounding shall be considered for the objectives that are assessed in both exposure groups:

- Comparative effectiveness design: primary objective 2, secondary objective 4, exploratory objectives CCI
- Descriptive patterns during follow-up in both exposure groups: secondary objectives 5 through 7

In the presence of confounding, the observed results on the outcomes in the compared exposure groups may be due to confounding factors, rather than due to the differing exposure status. Confounding may be a particular challenge in this study, because no active comparator could be identified, as discussed in [Section 3.3.1.1](#).

This risk of confounding will be addressed by matching the compared groups on PS, to emulate randomisation and to enhance the comparability of the exposure groups with regards to their characteristics at CED. Hence, the SOC/non-user group will be restricted to patients with similar prognostic factors and probability of receiving OM-85 during the initiation grace period.

The success of the PS matching (including only measured confounders) will be presented in the descriptive results on baseline characteristics. Similarity of the two exposure groups, i.e., equal distribution of patient characteristics influencing the occurrence of RTI episodes, will relieve uncertainty about the interpretation of the findings. Dissimilarity would warrant cautious interpretations.

As in all non-interventional studies, residual confounding may persist, especially concerning unmeasured confounders (such as lifestyle and health-seeking behaviours), or unknown confounders. Analyses for further addressing confounding analytically and/or investigating the presence of possible confounding (direction and magnitude of anticipated biases) will be considered in the SAP.

It should be noted that for secondary objectives 5-7, on pattern of prescribing antibiotics, concomitant medications of interest, and healthcare resource utilisation, no comparative analyses between the exposure groups will be performed (but may be performed as part of exploratory objectives **CCI**). The descriptive results in both exposure groups separately shall be interested considering possible differences in their baseline characteristics.

### **3.9.2 Information Bias**

Missing or incomplete data in the selected data sources or poor data validity may result in information bias. A feasibility assessment of the data sources was performed before designing the study, which supported the selection of available data with an overall good completeness and validity. Nonetheless, risk of misclassification of variable cannot be ruled out, as described below.

#### **3.9.2.1 Exposure Misclassification**

By large, the validity of the exposure assessment from the secondary data sources is expected to be high and risk of misclassification low. According to the conducted feasibility assessment, exposure to both OM-85 and the other bacterial lysates are generally available in the prescribing records of the data sources. However, drugs provided in hospitals are not captured. This possible exposure misclassification is not expected to hamper the result of the study, considering that the patient population is primarily treated in outpatient settings.

This study relies on prescription records, and no data are available regarding if the OM-85 prescription was dispensed to the patient or if the patient actually consumed OM-85. Hence, some patients classified as exposed to OM-85 may not actually have been exposed. This exposure misclassification would likely bias the results towards the null, i.e., the possible protective effect of OM-85 would be more difficult to detect, which shall be considered in the interpretations.

#### **3.9.2.2 Outcome Misclassification/Information Bias**

As this is a retrospective study using healthcare databases, diagnosis codes are used to capture RTIs. Based on the feasibility study, diagnosis codes for RTIs are captured in the data sources. Nonetheless, there is a possibility that not all RTI cases are recorded in the data sources, especially since the data sources do not represent all healthcare settings: THIN in Belgium and Italy represents exclusively primary care, and Inspur in China secondary/tertiary care. Overseeing some RTIs would result in underestimating the rate of RTI episodes, which in turn would likely bias towards the null, i.e., the possible protective effect of OM-85 is more difficult to detect, which shall be considered in the interpretations.

In addition, RTI episodes (primary outcome) are not directly available in the data sources, nor are the variables used in trials (43–46) to define RTI episodes. Therefore, RTI episodes are defined based on observed time between records of RTI diagnoses, 14 days (main RTI definition). While this maximum length of an RTI episode was developed in collaboration with clinicians, the duration could lead to underestimating or overestimating the true number of RTIs, which may differ depending on if a patient had mostly URIs or LRIs, as well as for children and other ages. The descriptive results on the type of infections recorded in baseline will provide further information on the validity of the time frame of an RTI episode for the study population.

Additionally, alternative definitions for RTIs using baseline data will be explored in Step 1 of the analysis, as detailed in Section 3.7.8: a simple and complication RTI definition (Section 3.3.2.1). A sensitivity analyses will also be performed for different lengths of RTI episodes, 7 and 21 days. These will inform about the robustness of the main RTI definition, to be considered in the interpretation of the results.

In the interpretations of the comparative results, the risk of detection or monitoring bias will have to be considered. Namely, the follow-up of the patients who initiate OM-85 may be more intensive than for the patients who did not, or for the same patient before initiating OM-85, as start of a new treatment typically triggers monitoring. This may result in increased *detection* of RTIs after initiating OM-85, while corresponding RTIs (especially less severe) could be undetected without an initiation of a new drug and its monitoring. However, considering the safety profile of OM-85, no extensive monitoring is expected. The descriptive results on healthcare resource utilisation will facilitate the interpretation of the results concerning the risk of monitoring bias, potentially increasing the detection of RTIs after initiating OM-85.

The comedications and antibiotic prescription at baseline and treatment patterns in follow-up on OM-85, antibiotics and concomitant medications of interest may be subject to outcome misclassification, because defining patterns of medication use will rely on assumptions. For example, a daily dose for OM-85 (e.g., one capsule per day) has to be defined (if not directly available) to estimate the duration of a prescription, and defining a duration of a treatment episode requires additional assumptions (e.g., maximum allowable gap between prescriptions that defines treatment discontinuation). These definitions are defined for OM-85 in Section 3.3.1.2, will be further detailed in the SAP, and sensitivity analyses may be considered with modified assumptions.

Vaccination status as a baseline variable cannot be assessed for all patients included due to data availability and time since vaccination (e.g., the study design cannot assess early childhood vaccination for elderly patients included in the population due to the maximum baseline period defined in each of the data sources), although it could decrease the number of RTI episodes. Therefore, exclusively vaccines that can be administered yearly, namely the influenza vaccines, are considered in this study for Belgium and Italy only. No vaccine information is available in Inspur (China). Some baseline comorbidities and diagnoses may not be adequately captured during the 12-month baseline period, due to the most recent diagnosis code being recorded

earlier, e.g., COPD being recorded 13 months before the CED. Therefore, the maximum baseline period will be used for assessing the presence of chronic conditions.

### 3.9.2.3 Misclassification of Other Variables

The classification of patients to subgroups based on diagnosis codes is subject to the same risk of misclassification as mentioned above for comorbidities and diagnoses. The use of the maximum baseline period mitigates this risk. Some of the subgroups were not part of the feasibility assessment, and therefore have a higher risk of misclassification. Specifically, misclassification is expected for food allergy and pregnancy. The subgroup of pregnant women may be over or underestimated, while the subgroup of patients with food allergy will likely be underestimated because some patients with food allergy would not have a corresponding record in the database. These limitations will have to be considered in the interpretation of the results.

### 3.9.3 Selection Bias

Selection bias refers to the selective inclusion of patients who are not representative of exposure or outcome in the source population, causing distortion in the exposure -outcome relation.

No selection bias is anticipated to emerge from the use of the healthcare databases, which were selected based on a thorough feasibility assessment. While the two European data sources include patients treated in primary care, this type of patients is limited in Inspur (China) where mostly secondary and tertiary care data are available. The combination of the three data sources will provide a wide coverage of the source population in terms of health settings.

Selection bias due to differing settings for the compared exposure groups is not a threat in this study, because both exposure groups are included from the same source populations and time periods, within each country. Further, no selection bias is anticipated to emerge from the application of the inclusion criteria, as availability and data quality of the inclusion criteria in the databases was assessed in the feasibility study.

Further, selection bias is reduced by including in the OM-85 exposure group exclusively patients initiating preventive treatment with OM-85, i.e., new users only, using the 12-month baseline period as a washout when no prescriptions of bacterial lysates are allowed. Including prevalent users (patients with a previous record of OM-85 in the 12-month baseline period) would have two implications:

- Healthy-user or adherer bias, as the included prevalent users would be patients who did not experience early adverse events or lack of early effectiveness.
- The effect against RTI would in reality start before the index date and this effectiveness would not be captured, and therefore the overall effectiveness of OM-85 could be decreased in the results.

By starting follow-up time at the end of the initiation grace period leads to left truncation, however since mortality due to RTI is low, potential for selection bias due to death in the initiation grace period would be low. Furthermore, it is possible that some patients may not match in PS matching; however, given known indications and contra-indications of OM-85, there should be similar patient characteristics in users and non-users and good overlap of PS to create a match. Sensitivity analysis using CCW methods, however, are planned and will use the entire cohort without exclusion and will have follow-up from CED, which will eliminate left truncation.

### 3.9.4 Time-Related Biases

Time-related biases were minimised by designing the study using the TTE framework (28,29). Importantly, follow-up was carefully selected to start at the end of the initiation grace period, equally for both exposure groups to eliminate immortal time bias. Starting follow-up at OM-85 initiation date for the OM-85 groups, and at CED for the SOC/non-user group would inevitably result in immortal time bias.

The initiation grace period was defined as 30 days, based on alignment with clinicians on a reasonable time for prescribers to prescribe preventive treatment with OM-85 after an RTI. Alternative grace periods may be considered in the SAP.

The time windows to detect the outcomes during the follow-up were chosen based on evidence from interventional studies on OM-85 with up to 12-month follow-up (24). In this study in real-world settings, follow-up was extended to 24 months, with the opportunity to investigate longer-term effectiveness and thereby complement the results of interventional studies. No bias is anticipated from this maximum 24-month window to detect outcomes.

The OM-85 treatment strategy was considered static (Section 3.3.1), based on its clinical use. However, in the static treatment strategy in the main analysis, OM-85 initiators will not be censored if/when they are prescribed other bacterial lysates during the follow-up. While this is consistent with the chosen treatment strategy, the time window for detecting the outcomes associated with OM-85 is not free from the effect of other bacterial lysates. Therefore, censoring follow-up at the first date of a prescription of another bacterial lysate will be applied in a sensitivity analysis, for both exposure groups.

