### 2.1 Primary Objectives

- **Primary objective 1: RTI rate 12 months before and 12 and 24 months after initiating OM-85:** To describe and compare the rate of RTIs episodes 12 months before initiating preventive treatment with OM-85 and 12 and 24 months after the initiation.
- **Primary objective 2: Comparative effectiveness – rate of RTI episodes during follow-up at 12 and 24 months:** To compare the rate of RTI episodes during the follow-up at 12 and 24 months, in patients initiating preventive treatment with OM-85 and in comparable patients not initiating OM-85 (SOC/non-user group).

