**Table 2 Events Ending Follow-up and Censoring Variables**

		Operational Definition
Events ending follow-up, throughout the follow-up		
1	End of 24-month follow-up	2 years from end of initiation grace period for each patient
2	Death	For THIN Italy and Belgium: last contact date, which defines exit from the database regardless of reason (death, physician change, or choosing to exit the database) For Inspur China: Date of death directly available by a report from social security sent to Inspur
3	Loss to follow-up/exit of data source	For THIN Italy and Belgium: last contact date, which defines exit from the database regardless of reason (death, physician change, or choosing to exit the database) For Inspur China: Date of lost to follow-up, which defines exit from the database regardless of reason (death or migration to another city)
Censoring during follow-up, after the 30-day initiation grace period: deviation from the assigned treatment strategy		
1.1	OM-85 group: None	-
1.2	SOC/non-user group: at first date of OM-85 prescription during follow-up (after the initiation grace period)	Same
1.3	Sensitivity analysis: The SOC/non-user group are censored at the first date of prescription for any bacterial lysate (including OM-85), the OM-85 group would be censored at the first date of prescription of any bacterial lysate other than OM-85 during follow-up	Same

Note: CED: cohort entry date; SOC: standard of care; THIN: The Health Improvement Network.

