#### 3.3.1 Exposures

To investigate the effectiveness of OM-85 using the TTE framework, the other clinically relevant treatment strategy that OM-85 will be compared to needs be defined, i.e., a treatment strategy that the patients prescribed OM-85 could alternatively have (28,29). This alternative treatment strategy to patients who initiated OM-85 is defined as “not initiating OM-85”, which will represent a SOC/non-user group (Table 6).

A 30-day initiation grace period starting from the CED will be applied for each included patient (Section 3.2.1), to allow the included patients to initiate OM-85 during a reasonable period after the CED, as it is unrealistic to expect that OM-85 would in clinical practice be prescribed on the date of meeting the eligibility criteria (28,29). Patients will be ascertained as treated or untreated depending on whether they received a prescription for OM-85 during the grace period.

After the patients have been categorised to one of the treatment strategies during the initiation grace period, the OM-85 treatment strategy will be considered static and no censoring will be applied due to “deviation from the treatment strategy”. Censoring at initiation of other treatments for RTI will not be applied, because patients initiating OM-85 are typically prescribed RTI

treatments as part of RTI treatment pathway, including symptomatic measures and/or antibiotics. In other words, patients in clinical practice may be prescribed other treatments in parallel with OM-85. Therefore, censoring at initiation of another therapy would not be a deviation from the OM-85 treatment strategy. Censoring OM-85 at discontinuation will also not be applicable, because OM-85 is not used continuously in clinical practice, but rather as 3-month or 6-month courses (consisting of monthly 10-days treatment periods). Consequently, all patients initiating OM-85 will be followed-up regardless of initiation or parallel use of other therapies.

The frequency of RTI episodes could be impacted by other treatments taken during the follow-up. However, it is likely that most patients co-medicate over the course of RTI episodes, which would lower the magnitude of effect. To address this limitation, the results will be interpreted considering observed other treatments than the index drug during the follow-up period.

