Comparative analysis comparing outcomes measured before and after OM-85 initiation will be performed in all patients assigned to OM-85 exposure group. The distribution of the outcomes measured before and after OM-85 initiation (including various follow-up windows per specified in each objective) will be presented. Generalised linear models will be used, with the flag that indicates before or after OM-85 initiation as the independent variable and the outcome of interest as dependent variable.

Comparative analysis comparing the two exposure groups (treatment strategies, i.e., OM-85, or SOC/non-user) will be performed among the PS-matched samples. The distribution of the outcomes measured in each exposure group and in various follow-up windows as specified in each objective will be presented. Generalised linear models will be used, with the flag that indicates exposure group assignment (i.e., OM-85 or SOC/non-user) as the independent variable and the outcome of interest as dependent variable.

For all the generalised linear models used, distribution and link functions that are appropriate to the type of outcome will be used. Offset will be applied when applicable. Estimated coefficients (or corresponding exponentiated estimates, e.g., IRR) of the independent variables with corresponding 95% CI and significance level (i.e., p-value) will be reported. Cluster-robust standard errors will be used in estimating CI and significance level, to account for correlated data.

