### **3.7.3 Analysis of Primary Endpoint: RTI Rates (Primary Objectives 1-2, Secondary Objectives 3-4, Exploratory Objectives CCI)**

The primary outcome is the rate of RTIs episodes measured during different periods of interest, as specified in the objectives. The rate of RTI episodes will be estimated by calculating the total number of RTI episodes observed, divided by the total number of person-time (e.g., person-years) during a period of interest. Rates of RTI episodes will be estimated separately in patients initiating preventive treatment with OM-85 and in the SOC/non-user group. Furthermore, rates of RTI episodes during the baseline period will serve as reference in each treatment group to evaluate the effects of therapy during follow-up.

Comparative analysis comparing the RTI rates before and after OM-85 initiation, and analysis comparing RTI rates in the two exposure groups will be performed using approaches as described in the General Considerations. Generalised linear models with a Poisson distribution or negative binomial distribution (to account for over-dispersion) will be used to estimate the association between the initiation of OM-85 and the outcome of RTI rates, with the natural logarithm of the time at risk as offset (42).

The analyses will be identical for the exploratory objectives **CCI** **CCI** (Section 3.2.2.3).

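### The 24-month rate ratio contains the whole first year, so it does not by itself show the longer-term effectiveness that the 24-month follow-up was meant to study; a months >12-24 contrast should be added

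*Protocol*

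**What the plan says.** Section 3.9.4 takes the outcome windows from interventional studies with at most 12 months of follow-up and explains that here "follow-up was extended to 24 months, with the opportunity to investigate longer-term effectiveness". It adds: "No bias is anticipated from this maximum 24-month window to detect outcomes".

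The contrasts are set elsewhere in the Protocol:

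- Section 2.1, primary objective 1, sets the rate in the period "12 months before initiating preventive treatment with OM-85 and 12 and 24 months after the initiation".
- Section 2.1, primary objective 2: "To compare the rate of RTI episodes during the follow-up at 12 and 24 months", OM-85 initiators against the SOC/non-user group.
- Table 2 ends follow-up at "2 years from end of initiation grace period for each patient". Table 3 starts the clock at OM-85 initiation for objective 1 and at the end of the grace period for objective 2.
- Section 3.7.3 defines the rate as total episodes "divided by the total number of person-time (e.g., person-years) during a period of interest" and models it with a log-time offset.
- Section 3.7.1 uses one before/after flag or one exposure flag. It says that outcome distributions "in various follow-up windows as specified in each objective will be presented".

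On treatment, section 3.3.1 says that "OM-85 is not used continuously in clinical practice, but rather as 3-month or 6-month courses". It treats the OM-85 strategy as static, with no censoring for deviation, while SOC/non-user patients are censored at their first OM-85 prescription.

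**The concern.** What 24 months of follow-up adds to the 12-month trials is months 12 to 24. A drug given in courses of 3 or 6 months makes it natural to ask whether any benefit lasts into the second year. The planned 24-month figure averages both years. A benefit confined to year 1 and a smaller benefit sustained over both years can give the same 0-24 month IRR. If that figure is read as longer-term effectiveness, the reading goes beyond what was estimated.

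For primary objective 2 there is a second ambiguity. The static OM-85 group mixes patients who had one course with patients re-treated in year 2, and the subgroups by treatment cycle in Table 5 are not assigned to that objective.

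**Working it through.** **Windows.** The word cumulative does not appear, but counting from time zero is the plain reading of section 2.1, Table 2 and the rate definition in section 3.7.3. No readable section names a 12-24 month interval or a time-by-exposure term. The exploratory objectives and sections 3.7.8 and 3.9.4.1 are largely redacted and cannot be checked.

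**The protocol's own precision figure.** Section 3.5 assumes 2 episodes per person-year and equal person-time, and gives an F-based CI. For 350 person-years and IRR 0.9, the counts are b = 2 × 350 = 700 and a = 0.9 × 700 = 630. The CI width is 0.197, as in Table 9. All 32 cells of Table 9 reproduce to three decimals.

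**Averaging over two years.** With a constant background rate, and s the year-2 person-time as a share of year-1 person-time:

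IRR(0-24) = (IRR year 1 + s × IRR year 2) / (1 + s)

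The year-specific IRRs and s are assumptions; the Protocol gives none. With a year-2 IRR of 1.00:

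| Year-1 IRR | s = 1.0 | s = 0.8 | s = 0.5 |
|---|---|---|---|
| 0.70 | 0.85 | 0.833 | 0.80 |
| 0.80 | 0.90 | 0.889 | 0.867 |
| 0.90 | 0.95 | 0.944 | 0.933 |

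Less year-2 person-time pulls the result towards the year-1 value. A steady IRR of 0.90 in both years also gives (0.90 + 0.90) / 2 = 0.90, the same as the year-1-only case in the middle row at s = 1.

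**Precision, primary objective 2.** Take year-1 IRR 0.80, s = 1, 2 episodes per person-year and an assumed 1,000 patients per group.

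- SOC episodes: b = 1,000 × 2 years × 2 = 4,000. OM-85 episodes: a = 0.90 × 4,000 = 3,600.
- SE(log IRR) = √(1/3,600 + 1/4,000) = 0.0230.
- 95% CI = 0.90 × exp(±1.96 × 0.0230) = 0.86 to 0.94.
- z = ln(0.90) / 0.0230 = -4.6. With two-fold over-dispersion, z = -4.6 / √2 = -3.2.
- Months >12-24 alone, with 2,000 episodes expected per group: IRR 1.00, 95% CI 0.939 to 1.064 by the protocol's F formula.

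At an assumed 0.5 episodes per person-year and 2,000 per group (a = 1,800, b = 2,000), the 0-24 month CI is 0.844 to 0.959.

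**Sensitivity to the assumptions.** Poisson chance that the 0-24 month CI excludes 1 although year 2 has no effect:

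| Year-1 IRR | 350 per group | 1,000 per group |
|---|---|---|
| 0.70 | 98.5% | >99% |
| 0.80 | 77% | >99% |
| 0.90 | 27% | 62% |

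Under a negative binomial variance with year-1 IRR 0.70 and 350 per group, the 0-24 month CI is 0.746-0.968 at dispersion 0.5 and 0.719-1.005 at dispersion 1.

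**Primary objective 1.** The averaging formula applies with the 12-month pre-initiation rate as reference. The CIs above do not carry over, because 12 months before are set against 24 months after.

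**The case against.** The strongest reply is that nothing in the estimand is wrong. An average rate over 0-24 months is legitimate, section 2.1 asks for it, and the longer-term wording is one clause in the limitations section, with no hypothesis or decision rule attached. That stands. A reader might infer that the 24-month half of the primary result is erroneous; the Protocol does not support this. It also nowhere commits to concluding that an effect persists in year 2.

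Second, the 12-month result sits beside the 24-month result. In the example a reader would see 0.80 and then 0.90, and with equal person-time could back out 2 × 0.90 - 0.80 = 1.00 for year 2. So a year-1-only effect would not be hidden. What is missing is a planned year-2 estimate with its own interval; the two reported estimates are nested and correlated, so that interval cannot be read off theirs.

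Third, a reader might infer that durability and re-treatment cannot be separated at all. That is too strong. Secondary objective 2 (Table 8) describes prescriptions, cycles and intervals up to 24 months, and Table 5 has cycle subgroups for primary objective 1. Those subgroups are conditional (section 3.2.2.3) and do not extend to primary objective 2, so the gap is confined to that objective.

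Fourth, a year-2 contrast has its own weakness. Matching balances characteristics at cohort entry, and SOC/non-user patients leave at OM-85 start (section 3.2.1, Table 2), so the comparison is conditional on remaining uncensored for a year. Resting longer-term statements on that interval alone would therefore go too far.

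Finally, the SAP is not shown and may add an interval analysis. The windows of the primary objectives are nevertheless fixed in this document.

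**Conclusion.** The point holds as a mismatch between a stated purpose and the planned contrasts, with a cheap remedy. It is not an error in the stated estimand. The 0-24 month IRR contains the whole 0-12 month window and alone does not show an effect beyond month 12.

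With full retention, a constant background rate and no year-2 effect, the distance of the IRR from 1 is halved: 0.80 in year 1 becomes 0.90 over 24 months. With 1,000 per group under Poisson variation that interval clearly excludes 1. Whether it does so in the actual data depends on group size, dispersion and the true year-1 effect, all assumed here; with small groups, strong over-dispersion or a weak year-1 effect it may well include 1.

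**What to change.** In sections 2.1 and 3.7.3, with detail in the SAP:

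1. Keep the 0-24 month IRR and label it the average effect over 24 months.
2. For both primary objectives, add the RTI rate and IRR with 95% CI for months >12-24, or an exposure-by-period (before/after-by-period) term that yields the same contrast.
3. State that effectiveness beyond 12 months will not be claimed from the 0-24 month IRR alone.
4. State that the year-2 contrast is less precise and conditional on remaining under follow-up, with SOC/non-user patients censored at OM-85 start. Read it with that selection in mind, for example with censoring weights as a check. The weighting in section 3.7.7 is described for censoring in the grace period, so year 2 would need its own specification.
5. For primary objective 2, show beside it the share of OM-85 patients with a further OM-85 prescription in months 12-24.

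Disjoint intervals for the 3-, 6- and 9-month secondary objectives are optional. The cost is wording and one extra table from data already held, plus the weighting model if used.
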